- 1) **To establish the feasibility** of reducing wave reflections while minimizing changes in brachial blood pressure. By performing assessments of the effects of 3 different doses of SR ISMN on office and 24-hour blood pressure and wave reflections, we aim to determine which dose of this drug best reduces wave reflections with the least impact on brachial blood pressure in this particular population. This will directly support secondary aim 1 of the RO1 application and will inform about the best dose to use in the definitive RO1-funded trial/application. We will also assess whether vitamin C reduces the tolerance to nitrate therapy over time.
- 2) We will gather preliminary data regarding the feasibility of using an **unbiased biomarker discovery approach** to identify biomarkers/pathways that change with ISMN administration in our 20 subjects. We will utilize a novel proteomic approach (Somasscan) to measure levels of 1,129 candidate biomarkers at baseline and after ISMN. We eventually want to identify novel biomarkers/pathways that correlate with the cardiac response to ISMN.
- 3) To assess the variability in changes in **aerobic capacity** (peak oxygen consumption during maximal supine bicycle exercise test), **vasodilatory reserve to exercise** (reduction in systemic vascular resistance with exercise, measured with Doppler echocardiography), and **physical activity** (assessed via actigraphy) with ISMN administration.

B. BACKGROUND AND SIGNIFICANCE

Heart failure (HF) is a major epidemic.

Heart Failure (HF) affects ~2.4% of the US population and 10% of individuals aged >75 years. The burden of HF has increased dramatically over the last few years, vastly exceeding previous projections (Figure 1). According to the American Heart Association^{13, 14} the number of new HF cases in the US increased from 348,000 in 2000 to 670,000 in 2007, representing a 93% increase over this time period. Not only is HF already an epidemic, but with the aging of the population, a dramatic further increase in its prevalence is expected.

Figure 1. The Epidemic of Heart Failure. Projected burden of HF in the US according to previous projectors (solid line) vs. actual burden (dotted line) From: Lam et al. European journal of heart failure. 2011;13:18-28

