
Figure 6. Hazard curves for incident of Heart Failure among 5,958 MESA participants stratified according to the presence or absence of hypertension (prevalence=45%) or the presence or absence of "high" reflection magnitude (top 45% of the population). Hazard curves are adjusted for other significant predictors of HF in this population. From: [name] JA et al, *J Am Coll Cardiol*: 60:2170-2177.

Targeting Central Hemodynamics in CKD Pilot Study
Protocol Version 003, February 15, 2016

highly desirable goal from the clinical and public health perspective. In order to design a definitive proof of concept trial, we must first establish the optimal dose of ISMN to reduce wave reflections independently of blood pressure and to assess the variability in study endpoints in response to ISMN in this particular population, such that adequate power calculations can be made.

C. RESEARCH DESIGN AND METHODS

C.1. Overview of study design

This is a pilot study in which we will study 20 subjects with CKD. We will perform a run-in phase in which the dose of sustained-release ISMN (SR-ISMN) will be increased from 30 to 120 mg over weeks. We will administer 30 mg for 1 week, followed by 60 mg for 1 week, followed by 120 for 1 week. At the end of each week, we will perform detailed assessments of blood pressure and central hemodynamics. We will assign half of the participants to receive vitamin C (500 mg three times daily) to assess whether this intervention reduces nitrate tolerance.

After the initial 3-week run in phase, we will randomly assign subjects to receive either 60 or 120 mg of SR-ISMN for additional 21 weeks (for a total of 24 weeks of therapy). Half of the subjects will continue to receive vitamin C (500 mg three times daily by mouth) throughout this 21-week period. We will assess the effect of our interventions on late systolic load, LV mass, LV fibrosis, diastolic relaxation and quality of life.

After subjects are identified and demonstrate an interest in the research study, inclusion and exclusion criteria will be assessed and if eligible, the patients will undergo written informed consent and enrolled in the study.

C.2 Study Sites

The two sites for this trial will be the Hospital of the University of Pennsylvania and the Penn Presbyterian Medical Center. Both sites share a single Institutional Review Board.

C.3. Study Population

[figure not shown]

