All data collected in this trial will be housed inside of a locked cabinet in the office space of the research staff, located at Ravdin 2 (Cardiovascular Institute).

C.8. Early termination

Subjects who withdraw due to intolerable adverse events or other safety concerns, or simply because they no longer wish to participate in the trial, will undergo a termination visit in which we will document: (1) vital signs; (2) compliance with the medications, including pill count; (3) Adverse effects. (4) specific reason for withdrawal.

D. Statistical Considerations

All study outcomes are continuous measures, thus, least-square regression models will be used to estimate effect sizes associated with each intervention. For the run-in phase, we will use mixed models to assess within subject changes to 30- 60 and 120 mg, and also to assess the effect of ascorbic acid on this response.

Analysis of the changes at 24 weeks between the study arms will also be assessed with mixed models to assess the following: (1) whether there are any significant within group changes in the outcome measures (from baseline to the final visit) in response to nitrate therapy at 30, 60 or 120 mg; (2) To test whether the outcome improvement in response to combination therapy is different between the 2 doses; (3) Whether vitamin C appears to have any effect on the responses. We recognize that this is a pilot study and therefore we will pay particular attention to the variability in the response and will interpret trends conservatively, particularly when confidence intervals are wide enough to be inconclusive. We note that, even though there is limited power for the inferential analyses, the data from this study will be critical to perform power calculations and propose a definitive trial, as per the aims of our R56 award. MRI endpoints will involve only 2 measures (baseline Targeting Central Hemodynamics in CKD Pilot Study

Protocol Version 003, February 15, 2016

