and 24-weeks). However, echocardiographic and tonometry measures will involve three measurements per subject during the long-term phase (baseline, 12-week and 24-week visit). These will be modeled for intervention effects using general linear modeling on the intent-to-treat population.^{64, 65} Subject-specific intercepts and slopes will be included as random effects; variability in the actual timing of assessments will be explicitly included in the mixed model by analyzing time as a random effect. Individual growth parameters will be modeled as a function of group, time, and the interaction of group and time. Differences in reflection magnitude over time will be examined via inferential testing of the “group by time” interaction term. Restricted maximum likelihood estimation will be used, and an appropriate covariance matrix will be specified. Linear and quadratic mixed models will be examined. The Akaike information criterion⁶⁶ will be used to evaluate overall model fit and to select the best-fitting longitudinal change pattern. For dropouts, the mechanism for missingness will be evaluated. If the number of subjects lost to follow-up is small and the missing observations can be documented as being missing at random (MAR) or missing completely at random (MCAR), analyses will be performed using the complete observed data. More complex approaches will be considered, such as random pattern-mixture models if necessary.^{67, 68} Sensitivity analyses for these models will be performed.⁶⁹ We will use parsimonious linear models to assess whether the reduction in reflection magnitude predicts the improvement in individual outcomes (LV mass, LV collagen volume fraction, LV diastolic relaxation velocity). Bootstrapping procedures will be used to obtain estimates of the effects and to test their significance via confidence intervals.⁷⁰ Analyses will be 1-tailed since we hypothesize specific directions to the relationships or changes in measured parameters between baseline and 24 weeks post-initiation of long-term therapy.

F. PROTECTION OF HUMAN SUBJECTS

F.1. RISKS TO THE SUBJECTS

Human Subjects Involvement and Characteristics

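### The long-term echo and tonometry model leaves out the on-drug week-3 visit, so no planned analysis estimates the change from week 3 to week 12; its AIC choice of time curve is also unsound if taken from REML likelihoods

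*Combined protocol and SAP*

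**What the plan says.** Section D has two models for the repeated measures. For the run-in, "we will use mixed models to assess within subject changes to 30- 60 and 120 mg", with vitamin C as a further factor. For the long-term phase, "echocardiographic and tonometry measures will involve three measurements per subject during the long-term phase (baseline, 12-week and 24-week visit"). That model has random intercepts and slopes, then: "Restricted maximum likelihood estimation will be used, and an appropriate covariance matrix will be specified. Linear and quadratic mixed models will be examined". AIC is used "to evaluate overall model fit and to select the best-fitting longitudinal change pattern". "Differences in reflection magnitude over time will be examined via inferential testing of the" group-by-time interaction. Among the questions listed for 24 weeks is "whether there are any significant within group changes in the outcome measures (from baseline to the final visit").

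Secondary aim 1 adds: "We will also assess whether vitamin C reduces the tolerance to nitrate therapy over time". Section C.1 gives the reason for assigning vitamin C to half the subjects: "to assess whether this intervention reduces nitrate tolerance".

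Section C.5 and the Appendix II schedule put tonometry and Doppler echo at week 3. Section C.4 computes reflection magnitude from those two signals, so it is available at weeks 0, 3, 12 and 24. By week 3 every subject is planned to be on 120 mg; dose is randomised to 60 or 120 mg only afterwards (C.1).

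**The concern.** Tolerance is a loss of effect while drug continues. Seeing it needs an early on-drug value compared with a later one at the same dose. Week 3 is the only early on-drug visit with reflection magnitude. The run-in model ends there and changes dose every week; the long-term model skips it. Each model holds one end of the comparison and neither holds both.

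The second issue is the curve. With three visits, a straight line cannot show that an effect levelled off or partly faded after week 12. The plan leaves line or curve to AIC, names REML as its only estimation method, and does not say which likelihood AIC uses. REML likelihoods from models with different fixed effects are not on a common scale.

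At stake is what the pilot tells the definitive trial about whether a response lasts. Mitral annular velocity, the echo measure among the co-primary endpoints, also goes through this model.

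**Working it through.** **Inputs.** From the documents: visits, 20 subjects, 10 per dose, 5 per dose-by-vitamin-C cell. The documents give no SD, effect size or power, so there is no figure of the plan's to reproduce. Assumed, in points of reflection magnitude: an 8-point fall; SD of intercepts 7, of slopes 3 per 24 weeks, residual *s* = 5 or 3.

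**1. What the long-term model can see.** A fall of 8 at week 3 that halves by week 12, and a constant fall of 4, both enter as (0, -4, -4). No choice of curve or likelihood separates them.

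**2. Effect of a linear fit** (least squares at weeks 0, 12, 24; slope per 12 weeks = (y24 - y0)/2):

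| Truth | Linear fit | Drawn as |
|---|---|---|
| Plateau (0, -8, -8) | (-1.3, -5.3, -9.3) | further 4-point fall after week 12 |
| Half waning (0, -8, -4) | (-2, -4, -6) | further 2-point fall; truth is a 4-point loss |
| Full waning (0, -8, 0) | -2.7 throughout | flat |

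Week 12 has zero weight in the slope, so 24 x slope equals the observed 0-to-24 change. This holds for complete data at nominal times; a middle visit at week 11 or 13 gets about 5-6% of week 24's weight.

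Error for the week 12-24 change, one arm (n = 10):
- Linear: SE = sqrt(9 + 2s²)/2/sqrt(10) = 1.21 or 0.82. With bias 4 (plateau) or 6 (half waning), RMSE is 4.1-4.2 or 6.1.
- Categorical visits: SE = sqrt(9/4 + 2s²)/sqrt(10) = 2.29 or 1.42, unbiased.

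**3. Time unit and REML-AIC.** In its usual form, -2 x REML log-likelihood contains ln|X'V⁻¹X|. Taking 4 weeks to the month divides t² by 16. Each quadratic column then changes that term by -2 ln 16 = -4 ln 4. With two such columns (t² and group-by-t²) the shift is 8 ln 4 = 11.1 in favour of the quadratic. The linear columns are in both models and cancel.

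**4. How often the quadratic is chosen** (simulated; ranges cover AIC counting all parameters or covariance parameters only):

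| Truth, residual SD | REML, weeks | REML, months | ML |
|---|---|---|---|
| Plateau, 5 | 10-23% | about 70-97% | about 90% |
| Plateau, 3 | 48-71% | about 95-100% | 100% |
| Half waning, 5 | 48-72% | 97-100% | 100% |
| Half waning, 3 | 98-100% | 100% | 100% |

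ML is not free of error: when the truth is a straight line it picks the quadratic in 17-18%.

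**5. Precision of the missing contrast.** SD of the week 3-to-12 change = sqrt((3 x 9/24)² + 2s²) = 7.16 or 4.39.
- 120 mg arm, n = 10: t(9) x SD/sqrt(10) = 5.1 or 3.1 points. With a common week-3 mean for the dose arms: 4.4 or 2.7.
- By vitamin C, 5 v 5: t(8) x SD x sqrt(2/5) = 10.4 or 6.4 points.

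**6. Gain from equating dose arms at weeks 0 and 3.** Known covariance, *s* = 5: Var(y24) = 49 + 9 + 25 = 83. Conditional on weeks 0 and 3 it is 43.1, against 9 + 50 = 59 for the change from baseline, so 27% lower. For *s* = 3: 21.1 against 27, 22% lower. Fitted simulations gave 28% and 13%.

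**The case against.** **Baseline might mean week 3.** Section D places its three measurements within the long-term phase, which begins after titration. On that reading week 3 is in the model. It is the less likely reading: C.5 starts drug after the baseline assessments, C.4 lists baseline and the 3-week visit as separate times, and Appendix II gives them separate columns. It would also leave the model with no pre-drug value and start the 60 mg arm from a 120 mg visit. The ambiguity is itself a reason to define the term.

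**The plan is not blind to tolerance.** The run-in model would show -8 or -4 at week 3, and Section D assesses vitamin C in the run-in and again at 24 weeks. A reader could set the two results side by side. That stands; what is missing is a planned contrast with its uncertainty.

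**The label.** A reader might infer that Appendix I places the loss between weeks 3 and 12, because 30 and 60 mg could not be told from placebo by day 42. It does not. Another comparison there has the 60 mg gain already about halved by day 14, and 120 mg was still significant at day 42. These are treadmill results in angina. They show that effect can fall over weeks of dosing, not when it would fall here.

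**The selection rates.** A reader might take the weeks column as what will happen. Section D names visits in weeks, Appendix II also calls them 3 and 6 months, and no model unit is stated. In months the rule mostly finds the curve.

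**Little is gained in 20 subjects.** The vitamin C contrast is too wide for inference, and Section D already promises caution. Both are true. They bear on how the result is read; leaving out data already scheduled does not follow from them.

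**Conclusion.** The omission of week 3 holds on the text, given that baseline is the pre-drug visit, and does not depend on any assumed SD or on how AIC is computed. No planned analysis estimates the week 3-to-12 change.

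The AIC point is conditional: it applies if the REML likelihood is used, which is the natural reading but is not stated. The 11.1-point unit shift is exact for the usual form of that likelihood with two groups; the percentages rest on the assumed SDs and effect.

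A stronger reading, that the 24-week findings are compromised, is not supported. The baseline-to-week-24 change has the same estimate and SE (2.4 or 1.6 per arm) under linear or categorical time, and the two-visit MRI endpoints involve no curve selection. Nor is waning always drawn as improvement: full waning is drawn flat, and half waning is often caught even in weeks. In a 20-subject variability pilot this lies between a point to consider and one that should be fixed.

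**What to change.** In Section D:

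- Define baseline as the pre-drug visit.
- Model visit as categorical (0, 3, 12, 24 weeks), keeping the random intercept and slope on actual time. This removes the AIC step. If polynomials are kept, compare them by ML and refit the chosen one by REML.
- Dose is randomised after week 3, so set the dose-arm means equal at weeks 0 and 3. Vitamin C is assigned at the start, so set its means equal at week 0 only.
- Report the week 3-to-12 and week 3-to-24 changes in the 120 mg arm, among subjects on 120 mg at week 3, with confidence intervals and as description. The split by vitamin C is descriptive only.
- State that the 60 mg arm's change from week 3 mixes dose change with tolerance and is not read as tolerance, and that loss before week 3 is not captured.

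Cost: analysis wording; no added visit or test. With two dose groups the mean model has 8 parameters, against 4 (linear) or 6 (quadratic); 6 with the dose arms equated at weeks 0 and 3, and 9 once additive vitamin C effects are included. Actual visit timing stays only in the random slope, and the week 12-24 interval is wider than a linear fit would give.

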- Ascorbic acid: Vitamin C, also known as ascorbic acid, is available over the counter. Some studies have shown that higher blood levels of vitamin C are associated with lower risk of death from all-causes, cancer, and cardiovascular disease.^{54, 55, 71} In patients with diabetes, some studies suggest that vitamin C supplementation reduces the risk, whereas others suggest that it increases the risk, of cardiovascular disease.^{54, 55, 71} Despite the multiple studies, there is no evidence that vitamin C supplements exert benefit in this patient population. However, there is no evidence of harm, with excellent tolerability with doses up to 2-10 grams/day in adults) exert any adverse or toxic effects. An upper level of 2 grams/day is recommended in order to prevent some adults from experiencing diarrhea and other gastrointestinal symptoms. In this study, we will use a dose of 500 mg three times daily, which is below this dose. Potential risks of discomforts include diarrhea, nausea, vomiting, heartburn, stomach cramps and headache. Such symptoms are not generally serious. Vitamin C may interact with warfarin, may increase the risk of oxalate kidney stone recurrence and may precipitate hemolysis in patients with glucose-6-phosphate dehydrogenase (G6PD) deficiency.⁷² Patients with either of these conditions will be excluded from the study. If patients experience any gastrointestinal symptoms or intolerance to vitamin C, we will reduce the dose to 500 mg bid, or 500 mg once daily. If vitamin C is still not tolerated, we will discontinue vitamin C, but subjects may remain in the trial taking only the assigned dose of ISMN-SR.

- (6) **Ambulatory blood pressure monitoring** may cause discomfort in the arm during cuff inflations but no serious risks are associated with this procedures. Ambulatory pulse wave analysis (Aurora device) may cause mild discomfort in the wrist.
- (7) During various procedures (cardiac MRI, echocardiography), we will **use adhesive electrodes** attached to the participant's skin to record the electrical signal from the heart. These may occasionally cause skin itching and irritation.
- (8) As with any clinical research study, there is a potential for breach of confidentiality. Adequate measures will be taken to minimize this risk (below).

These potential risks have been thoroughly considered and adequate protective measures will be implemented in the study (please see below).

F. 2. ADEQUACY OF PROTECTION AGAINST RISKS

c. Protection against risks associated with gadolinium contrast: Serum creatinine will be measured prior to each scan to assure adequate renal function for the administration of gadolinium-based contrast as per our inclusion/exclusion criteria. Pregnancy status will be determined for all women of childbearing age before enrollment and before the final MRI scan. Pregnant women will be excluded and/or discontinued from the study. Subjects will not receive two injections of gadolinium within one week of each other as frequent use of gadolinium can cause nephrogenic systemic fibrosis (NSF). If a subject has recently received an MRI for clinical purposes, the research MRI will be delayed to avoid the second injection of gadolinium within the one week-timeframe.

d. Protection against risks of study medications: To reduce the risk of hypotension and related side effect, participants will be instructed to get up slowly when rising from a sitting or lying position. The study team will specifically assess for the presence of Targeting Central Hemodynamics in CKD Pilot Study

Protocol Version 003, February 15, 2016

hypotension and orthostatic hypotension, as well as symptoms such as dizziness after the medication is initiated or after the dose is increased, in order to determine whether it is safe for participants to continue taking these medications, or to uptitrate the dose. If participants find these side effects too uncomfortable, they will be deemed intolerant to the drugs and discontinued from the study. Study subjects can always withdraw from the study at any time and this will be made clear to them. We will specifically exclude individuals who are taking sildenafil (Viagra®), tadalafil (Cialis®), or vardenafil (Levitra®) and we will instruct them not to take these medications while participating in the study, as well as the risks associated with this combination. If subjects express the wish to take these medications within the 24 weeks following consent, they will not be included in the study. We will exclude subjects with a history of kidney stones, since vitamin C may precipitate the recurrence of oxalate kidney stones. We will also exclude patients with G6PD deficiency, since vitamin C may precipitate hemolysis in this condition.^{72, 73}

e. Measures to minimize the risk of breach in confidentiality: All records will be treated with strict confidentiality according to HIPAA guidelines (all study personnel are trained on HIPAA regulations). Blood samples obtained from subjects will be used only for research purposes. Records will be treated with strict confidentiality and stored in a secured, limited access area. A subject ID number rather than name will identify all collected samples and images. A secure database of patient information will be maintained. Only the investigators will have access to research information and will follow IRB and institutional HIPAA guidelines. Paper files will be saved under lock in a secure IRB-approved area.

f. Other measures to minimize risk: Phlebotomy, arterial tonometry and Doppler echocardiographic examinations will only be performed by appropriately trained personnel as per our institutional standards. These procedures will be performed in CTRC-based cardiovascular phenotyping unit at either HUP or Penn Presbyterian medical center.

F.3. POTENTIAL BENEFITS OF THE PROPOSED RESEARCH TO THE SUBJECTS AND OTHERS

There are no anticipated direct benefits to the subjects as a result of their participation in this study nor will this be implied when obtaining consent. However, if our hypothesis is correct, subjects in the active medication groups may experience improvements in their LV hypertrophy and fibrosis, which are associated with the risk of heart failure. However, any potential benefit will not be implied during informed consent or enrollment. The results of this study may ultimately lead to an effective strategy to prevent HF in CKD, which is urgently needed. Since there is minimal risk and potential benefits to medical knowledge and society, the risk / benefit ratio is acceptable.

Overall, the minimal risk to human subjects for participation in this study is greatly Targeting Central Hemodynamics in CKD Pilot Study
Protocol Version 003, February 15, 2016

outweighed by potential scientific knowledge that may result from this work.

F. 4. IMPORTANCE OF THE KNOWLEDGE GAINED

If our hypothesis of a causal role is correct, this study may identify a potential intervention to induce reserve remodeling and prevent incident heart failure in CKD patients. Furthermore, if targeting wave reflections improves diastolic function, LV remodeling and the clinical status of CKD patients, this would lead to a better understanding of the mechanisms that lead to, or contribute to, cardiac dysfunction in CKD, which will accelerate the discovery of new treatments for this condition.

G. DATA AND SAFETY MONITORING PLAN

1. Adverse events

The Principal Investigator will be responsible for ensuring that all adverse events are noted, followed and reported to the IRB and DSMB as appropriate. The PI will continuously supervise all aspects of the study and review the records of the study subjects following each visit and at the end of their participation. Any adverse events (AE) will be rated on a 0-5 scale (0-no AE; 1-mild AE, no treatment required; 2-moderate AE that responds to treatment; 3-severe AE that would limit normal activities and require a prolongation of hospitalization; 4-life-threatening or disabling AE; 5-Fatal AE). Any AE rated ≥ 3 will be immediately reported to the IRB. All AEs will be reported to the IRB on an annual basis. In the case of a serious AE, the IRB will make a determination about the necessity to modify the protocol, include additional information in the consent form, inform previous participants, temporarily hold enrollment of patients, or terminate the study. All study procedures and cumulative adverse events are subject to full committee review at least yearly.

Adverse events known to be associated with ISMN include:

- Headache
- Mild dizziness
- Warmth, redness, or tingly feeling under skin
- Pounding heart beat
- Dry mouth
- Nausea/Vomiting
- Sweating
- Feelings of passing out
- An allergic reaction to this drug is very rare, but could manifest as hives, difficulty breathing, or swelling of the face, lips, tongue, or throat.
- Symptomatic hypotension.

Adverse effects that may be associated with vitamin C include:^{54, 55}

- Diarrhea
- Nausea
- Vomiting
- Heartburn
- Stomach cramps
- Headache

